6.6. Lifestyle And/or Dietary Restrictions

6.6.1. Contraception Requirements

Subjects with female partners of child-bearing potential must use condom while the female partner must use a highly effective contraceptive, such as IUD, birth control pills or diaphragm with spermicide, after the first dose of study treatment and until the end of study visit (for female partners) and during an additional 90 days period (for subjects themselves).

6.6.2. Meals and Dietary Restrictions

The first dose of the study drug in the morning will be done in the fasting state. Subjects will be required to fast from all food and drink with the exception of water for 8 hours prior to study drug administration. Water is permitted and may be consumed ad libitum post-dosing with a minimal intake of 2L/day to assure a sufficient diuresis, distributed as follows: 500 mL between dosing and T4H, 1000 mL between T4H and T12H and 500 mL between T12H and T24H.

Moreover, subjects will be asked on Day-1:

- To ensure sufficient hydration (around 2L over the 24-hour period) with a normal salt intake,
- To refrain from any fruit juice and sparkling water,
- These recommendations will be maintained during the hospitalization period.

In the SAD part, a standard lunch will be provided approximately 4 hours post-dosing. Dinner will be served 14 hours post morning dose (2 hours after the evening administration and after completion of assessments scheduled at this time from Cohort 2).

In the MAD part, a breakfast will be provided 2 hours post-morning dose, standard lunch 5 hours post-morning dose, a snack 9 hours post-morning dose and a dinner will be served 2 hours post-evening dose. Therefore, breakfast will be served at 10 AM, lunch at 1 PM, snack at 5 PM and dinner at 10 PM

Subjects will be requested to abstain from consumption of grapefruit or grapefruit-containing products) for 7 days prior to first dosing and until the follow up visit.

6.6.3. Caffeine, Alcohol

During each dosing session, subjects will abstain from alcohol and xanthine-containing beverages (e.g. coffee, tea, cola drinks, chocolate) for 24 hours prior to the start of dosing until collection of the final pharmacokinetic sample during each session.

6.6.4. *Activity*

Subjects will abstain from strenuous exercise for 48 hours prior to each blood collection for clinical laboratory tests. Subjects may participate in light recreational activities during studies (e.g., watch television, read).

6.7. **Total volume of blood collected**

Blood samples will be obtained according to the following schedule:

6.7.1. *SAD part: Collection schedule and Blood volume*

➤ Screening Visit (D-21 to D-2)

Biochemistry, Hematology, Coagulation, Serologies (5+2+4+8.5 mL)

Total = 19.5 mL

➤ Admission Visits D-1

Biochemistry, Hematology, Coagulation (5+2+4 mL)

Total = 11 mL

➤ Dosing Visit D1

PK samples: 14 samples (14 x 8 mL)

Exploratory biomarkers samples: 2 samples ([3+2.5 mL] x 2)

Total = 123 mL

➤ D2

PK samples: 2 samples (Cohort 1) (2 x 8 mL), 3 samples (Cohorts 2 to 6) (3 x 8 mL)

Exploratory biomarkers samples 1 sample (3+2.5 mL)

Biochemistry, Hematology, Coagulation (5+2+4 mL)

Total = 32.5 mL (Cohort 1), 40.5 mL (From Cohort 2 to 6)

➤ Follow up visit

Biochemistry, Hematology, Coagulation (5+2+4 mL)

Total = 11 mL

Total on the overall duration of the study: 197 mL (Cohort 1) and 205 mL (Cohorts 2 to 6)

6.7.2. *MAD part: Collection schedule and Blood Volume*

➤ Screening Visit (D-21 to D-1)

Biochemistry, Hematology, Coagulation, Serologies (9+2+2.7+5 mL)

Total = 18.7 mL

➤ Admission Visits D-1

Biochemistry, Hematology, Coagulation (5.5+2+2.7 mL)

Total = 10.2 mL

- Dosing Visit D1
PK samples: 12 samples (12 x 8 mL)
Total = 96 mL
- Dosing Visit D2
PK samples: 4 samples (4 x 8 mL)
Total = 32 mL
- Dosing Visit D3
Biochemistry, Hematology, Coagulation (5.5+2+2.7 mL)
Total = 10.2 mL
- Dosing Visit D6
Biochemistry, Hematology, Coagulation (5.5+2+2.7 mL)
Total = 10.2 mL
- Dosing Visit D7
PK samples: 3 samples (3 x 8 mL)
Total = 24 mL
- Dosing Visit D10
Biochemistry, Hematology, Coagulation (5.5+2+2.7 mL)
Total = 10.2 mL
- Dosing Visit D13
Biochemistry, Hematology, Coagulation (5.5+2+2.7 mL)
Total = 10.2 mL
- Dosing Visit D14
PK samples: 12 samples (12 x 8 mL)
Total = 96 mL
- Dosing Visit D15
PK samples: 7 samples (7 x 8 mL)
Total = 56 mL
- Dosing Visit D16
PK samples: 2 sample (2 x 8 mL)
Total = 16 mL
- Dosing Visit D17
Biochemistry, Hematology, Coagulation (5.5+2+2.7 mL)
Total = 10.2 mL
- Follow up visit
Biochemistry, Hematology, Coagulation (5.5+2+2.7 mL)
Total = 10.2 mL

Total on the overall duration of the study: 410.1 mL

7. COMPLETION OR EARLY WITHDRAWAL OF SUBJECTS

7.1. Subject Completion

A completed subject is one who has completed all phases of the study including the follow-up visit.

The end of the study is defined as the last subject's last visit.

7.2. Subject Withdrawal Criteria

Refer to Section [3.4](#) for dose adjustment/stopping criteria based on safety and PK criteria.

A subject may withdraw from study treatment at any time at his own request, or may be withdrawn at any time at the discretion of the investigator for safety, behavioral or administrative reasons.

7.3. Subject Withdrawal Procedures

In the event a randomized subject is withdrawn from the study for any reason, the Investigator should make every effort to perform a final study visit 7 to 14 days after last administration of investigational product and complete the assessments and procedures outlined in the Time & Events Table for 'Follow Up'.

Subjects who withdraw due to an AE(s) must have the AE followed as indicated in Follow-Up of AEs/SAEs.

Subjects who withdraw may be replaced at the discretion of the sponsor's team in consultation with the investigator.

8. ADVERSE EVENTS (AE) AND SERIOUS ADVERSE EVENTS (SAE)

The investigator or site staff is responsible for detecting, documenting and reporting events that meet the definition of an AE or SAE.

AEs will be collected from the signature of Informed Consent and until the follow-up visit.

This period will be extended on all on-going AEs after the last visit until all AEs are finally resolved.

SAEs will be collected over the same time period as stated above for AEs.

There is no time limit on the collection of SAEs that are considered related to study drug. Nevertheless and by default, the collection of SAE is primarily set as 1 month after the end of study participation. If the Investigator detects an SAE in a study subject after the end of the period of observation, and considers the event possibly related to prior study treatment

or procedures, he must contact the sponsor to determine how the SAE should be documented and reported.

8.1. Definitions of Adverse Events and New Facts

❖ Definition of an Adverse Event

An AE is **any untoward medical occurrence** in a patient or clinical investigation subject, temporally associated with the use of a medicinal product, whether or not considered related to the medicinal product.

An AE can therefore be any unfavorable and unintended sign (including an abnormal laboratory finding), symptom, or disease (new or exacerbated) temporally associated with the use of a medicinal product.

Events meeting the definition of an AE **include**:

- Any abnormal laboratory test results (hematology, coagulation, clinical chemistry, or urinalysis) or other safety assessments (e.g., ECGs, vital signs measurements), including those that worsen from baseline, and felt to be clinically significant in the medical and scientific judgment of the investigator.
- Exacerbation of a chronic or intermittent pre-existing condition including either an increase in frequency and/or intensity of the condition.
- New conditions detected or diagnosed after study treatment administration even though it may have been present prior to the start of the study.
- Signs, symptoms, or the clinical sequelae of a suspected interaction.
- Signs, symptoms, or the clinical sequelae of a suspected overdose of either study treatment or a concomitant medication (overdose per se will not be reported as an AE/SAE unless this is an intentional overdose taken with possible suicidal/self-harming intent; this should be reported regardless of sequelae).

❖ Treatment Emergent Adverse Event and Repetition of Adverse Event

- A treatment-emergent AE is any AE that occurs after dosing, or that was present prior to dosing but is exacerbated after dosing.
- AE occurring after subject enrolment (ICF signature) but prior to first study drug administration will be recorded as a non-treatment emergent adverse event (NTEAE).
- A clinically relevant worsening of an AE (e.g., relevant change in severity, seriousness) must result in a new entry. The original entry remains unresolved and is given an end date reflecting the date of the worsening and a comment must be entered stating that the AE is continuing with a changed severity/seriousness (e.g., "continues as event name with onset date and new severity/seriousness"). The onset date of the new entry is also the date of worsening.

❖ Events **that do not meet** the definition of an AE include:

- Medical or surgical procedure (e.g., endoscopy, appendectomy); the condition that leads to the procedure is an AE.
- Situations where an untoward medical occurrence did not occur (social and/or convenience admission to a hospital).
- Anticipated day-to-day fluctuations of pre-existing disease(s) or condition(s) present or detected at the start of the study that do not worsen.

❖ **Definition of New Facts**

A New Fact is defined as an incident, experience, or outcome that generally will warrant consideration of changes to the protocol or consent in order to protect the safety, welfare, or rights of participants. A New Fact may warrant corrective actions. Examples of corrective actions or changes that might need to be considered include:

- Modification of inclusion or exclusion criteria to mitigate the newly identified risks
- Implementation of additional safety monitoring procedures
- Suspension of enrollment of new participants or halting of study procedures for enrolled participants
- Modification of informed consent documents to include a description of newly recognized risks
- Provision of additional information about newly recognized risks to previously enrolled participants.

The sponsor informs immediately the competent authorities of those new events and the measures taken and ensure that the Ethics Committee is notified at the same time (France: ANSM, CPP, ARS).

8.2. **Definition of Serious Adverse Events**

❖ **General definitions**

A SAE or Serious Adverse Drug Reaction (ADR) is any untoward medical occurrence that at any dose:

- Results in death
- Is life-threatening (refers to immediate risk of death as the event occurred)
- Requires inpatient hospitalization or prolongation of an existing hospitalization
- Results in a persistent or significant disability or incapacity (defined as a substantial disruption in a person's ability to conduct normal life functions)
- Is a congenital anomaly or birth defect

Additionally, **important medical events** may be considered SAEs when, based on appropriate medical judgment, they may jeopardize the subject and may require medical or surgical intervention to prevent one of the outcomes listed in this definition. Examples of

such events include allergic bronchospasm requiring intensive treatment in an emergency room or at home, blood dyscrasias or convulsions that do not result in hospitalization, or development of drug dependency or drug abuse.

NOTE: In general, hospitalization signifies that the subject has been detained (usually involving at least an overnight stay) at the hospital or emergency ward for observation and/or treatment that would not have been appropriate in the physician's office or out-patient setting. Complications that occur during hospitalization are AEs. If a complication prolongs hospitalization or fulfills any other serious criteria, the event is serious.

Hospitalization for elective treatment of a pre-existing condition that did not worsen from baseline is not considered an AE.

8.3. **Expected and unexpected adverse events**

As this is a first-in-man (FIM) study, no AEs are defined as expected in humans.

Potential adverse reactions were identified from findings in the non-clinical toxicity studies and are mentioned in the Section 1.3 "Summary of Risk Management".

According to the French legislation and to the directives of the Health Authority (ANSM: "Obligations de déclarations immédiates du promoteur" Mai 2017), in a FIM study, a serious adverse drug reaction is considered as a New Fact and **New Facts identified by the Investigator are to be notified without delay to the sponsor.**

In case of New Facts, the administrations of the IMP will be withheld for all subjects, emergency measures will be implemented. The Authorities (ANSM, CPP and ARS) will be notified without delay by the sponsor's representative.

In the event of a suspension of the trial, before restarting, the subjects will have to be informed and, when needed, to sign a new ICF approved after amendment of the study.

8.4. **Method of Detecting AEs and SAEs**

Care will be taken not to introduce bias when detecting AEs and/or SAEs. Open-ended and non-leading verbal questioning of the subject is the preferred method to inquire about AE occurrence. Appropriate questions include:

- "How are you feeling?"
- "Have you had any (other) medical problems since your last visit/contact?"
- "Have you taken any new medicines, other than those provided in this study, since your last visit/contact?"

Subjects will be provided with a study card containing important information on the study particularly contact of the study staff (investigator) and an emergency phone number to be contacted 24/24 with a physician of the clinical center on duty.

8.5. Recording of AEs and SAEs

When an AE/SAE occurs, it is the responsibility of the investigator to review all documentation (e.g., hospital progress notes, laboratory, and diagnostics reports) relative to the event. The investigator will then record all relevant information regarding an AE/SAE in the appropriate pages in the CRF.

The investigator will attempt to establish a diagnosis of the event based on signs, symptoms, and/or other clinical information. In such cases, the diagnosis will be documented as the AE/SAE and not the individual signs/symptoms.

The following will also be specified:

- Other actions (none, medication required, tests required, hospitalization required or prolonged, treatment unblinded, other-specify)
- Outcome and date of outcome according to the following definitions:
 - Recovered/resolved
 - Recovering/resolving
 - Not recovered/not resolved
 - Recovered with sequelae/resolved with sequelae
 - Fatal
 - Unknown
- Seriousness: yes or no (criteria for SAE see above)

8.6. Evaluating AEs and SAEs

8.6.1. *Assessment of Intensity*

The investigator will make an assessment of intensity for each AE and SAE reported during the study and will assign it to one of the following categories:

- ❖ Mild: An event that is easily tolerated by the subject, causing minimal discomfort and not interfering with everyday activities (Grade 1).
- ❖ Moderate: An event that is sufficiently discomforting to interfere with normal everyday activities, no treatment except paracetamol (Grade 2).
- ❖ Severe: An event that prevents normal everyday activities or requires treatment (Grade 3).

An AE that is assessed as severe will not be confused with an SAE. Severity is a category utilized for rating the intensity of an event; and both AEs and SAEs can be assessed as severe.

8.6.2. *Assessment of Causality*

The investigator has to assess the relationship between study treatment and the occurrence of each AE/SAE.

The relationship of an AE to the IMP is based on all available information at the time of the completion of the CRF and is graded as follows:

- **Not related:** a reaction for which sufficient information exists to indicate that the etiology is unrelated to the study drug; the subject did not receive the study medication or the temporal sequence of the AE onset relative to administration of the study medication is not reasonable or the event is clearly related to other factors (subject's clinical state, therapeutic intervention or concomitant therapy).
- **Unlikely:** Does not follow a reasonable temporal sequence from administration of the IMP, or is most likely related to another etiology than the trial drug such as the patient's clinical state, environmental factors or other therapies.
- **Possibly:** a clinical event, including laboratory test abnormality, with a reasonable time sequence to administration of the drug but which could also be explained by concurrent disease or other drugs or chemicals.
- **Probably:** a clinical event including laboratory test abnormality, with a reasonable time sequence to administration of the drug, unlikely to be attributed to concurrent disease or other drugs and which follows a clinically reasonable response on withdrawal (de-challenge).
- **Definitely:** a reaction that follows a reasonable temporal sequence from administration of the drug, or in which the drug level has been established in body fluids or tissues, that follows a known or expected response pattern to the suspected drug, and that is confirmed by improvement on stopping or reducing the dosage of the drug, and reappearance of the reaction on repeated exposure (re-challenge if applicable).

8.7. Follow-up of AEs and SAEs

After the initial AE/SAE report, the investigator is required to proactively follow each subject at subsequent visits/contacts. All AEs and SAEs will be followed until resolution.

8.8. Prompt Reporting of SAEs to the sponsor

Once the investigator determines that an event meets the protocol definition of an SAE, the SAE will be reported to the sponsor **without delay, within 24h**.

Any follow-up information on a previously reported SAE will also be reported to the sponsor within 24 hours.

The SAE form must be completed and faxed [[contact]] or emailed [email: [contact]] to Stragen Services. Stragen Services acknowledges the receipt of the SAE information by email to the investigational site within one working day. In the absence of email acknowledging the receipt or in case of issue in sending the fax or email, the investigator shall contact Stragen Services by any means for ensuring the receipt of SAE information at the earliest opportunity.

The initial report must be as complete as possible, including details of the Serious Adverse Event, and most importantly an assessment of the causal relationship between the SAE and the study medication. Information not available at the time of the initial report (e.g., end date of the Serious Adverse Event or laboratory values received after the report) must be documented on a follow-up “SAE report form”.

The SAE report form and the instructions on completion are provided in the investigator’s study file.

8.9. Pregnancy

Because the effect of the study drug on sperm is unknown, pregnancies in partners of male subjects included in the study will be reported by the study-site personnel within 24 hours of their knowledge of the event using the SAE form.

Follow-up information regarding the outcome of the pregnancy and any postnatal sequelae in the infant will be required. For this purpose, follow-up requests will be initiated by Stragen Services, at the end of each trimester of the pregnancy and at least until delivery, using a specific Pregnancy Form.

Abnormal pregnancy outcomes (e.g., spontaneous abortion, fetal death, stillbirth, congenital anomalies, and ectopic pregnancy) are considered SAEs and must be reported using the Serious Adverse Event Form.

8.10. Liver chemistry Follow-up procedures

Refer to the diagram in Appendix 1 for a visual presentation of the procedures listed below.

The procedures listed below are to be followed if a subject meets the liver chemistry stopping criteria defined in Section [3.4.3.1](#):

- Immediately withdraw the subject from study treatment.
- Notify the medical monitor of the sponsor within 24 hours of learning of the abnormality to confirm the subject’s study treatment cessation and follow-up.
- Complete the “Safety Follow-Up Procedures” listed below.
- If the event also meets the criteria of an SAE (see Section 8.2), all remaining subjects of the cohort will be informed immediately, and the IMP administration immediately stopped. The sponsor will be notified without any delay. The SAE form will be completed with the relevant details.

Safety Follow-Up Procedures for subjects with ALT \geq 3xULN:

- Monitor subjects weekly until liver chemistries (ALT, AST, alkaline phosphatase, bilirubin) resolve, stabilize or return to within baseline values.

Safety Follow-Up Procedures for subjects with ALT \geq 3xULN and total bilirubin \geq 2xULN (>35% direct bilirubin); or ALT \geq 3xULN and INR > 1.5:

- This event is considered an SAE (see Section 8.2). Serum bilirubin fractionation should be performed if testing is available. If fractionation is unavailable, urinary bilirubin is to be measured via dipstick (a measurement of direct bilirubin, which would suggest liver injury).
- All remaining subjects of the cohort will be informed immediately and the IMP administration immediately stopped. The sponsor will be notified without any delay.
- Make every reasonable attempt to have subjects return to the clinic within 24 hours for repeat liver chemistries, additional testing, and close monitoring (with specialist or hepatology consultation recommended).
- Monitor subjects twice weekly until liver chemistries (ALT, AST, alkaline phosphatase, bilirubin) resolve, stabilize or return to within baseline values.

In addition, for all subjects with ALT \geq 3xULN, every attempt must be made to also obtain the following:

- Viral hepatitis serology including:
 - Hepatitis A IgM antibody.
 - Hepatitis B surface antigen and Hepatitis B Core Antibody (IgM).
 - Hepatitis C RNA.
 - Cytomegalovirus IgM antibody.
 - Epstein-Barr viral capsid antigen IgM antibody (or if unavailable, obtain heterophile antibody or monospot testing).
 - Hepatitis E IgM antibody.
- Blood sample for pharmacokinetic (PK) analysis. Record the date/time of the PK blood sample draw and the date/time of the dose of study treatment prior to blood sample draw on the source documents and the CRF.
- Serum creatine phosphokinase (CPK) and lactate dehydrogenase (LDH).
- Fractionate bilirubin, if total bilirubin \geq 2xULN.
- Assess eosinophilia.
- Record the appearance or worsening of clinical symptoms of hepatitis (fatigue, nausea, vomiting, right upper quadrant pain or tenderness, fever, rash or eosinophilia) on the AE CRF.
- Record use of concomitant medications, on the appropriate pages of the CRF.

The following are required for subjects with ALT \geq 3xULN **and** bilirubin \geq 2xULN (>35% direct) but are optional for other abnormal liver chemistries:

- Anti-nuclear antibody, anti-smooth muscle antibody, and Type 1 anti-liver kidney microsomal antibodies.
- Liver imaging (ultrasound, magnetic resonance, or computerized tomography) to evaluate liver disease.

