at the upper dose tested. IFB-088 was localized in the crystals observed in each kidney from each treated animal whereas IFB-139 metabolite was distributed in the entire kidney tissue with the most intense signals localized in the crystals.

In Beagle dogs, twice daily administration for 28 days was well tolerated up to 9mg/kg (NOAEL in this species) without any renal findings suggesting that when administered twice daily IFB-088 is better tolerated than when daily administered.

A twice-daily administration is thus proposed from cohort 2 and an appropriate monitoring plan will be set up with a regular check of renal function parameters (creatinine, urea, estimated Glomerular Filtration Rate and urinary dosage of Beta2 microglobulin, proteins and creatinine), volume of diuresis and urinary parameters by dipstick (pH, hematuria). An increased excretion of beta2microglobulin in the urine is a sensitive indicator of proximal tubular dysfunction (Ostermann M., Joannidis M (2016).

A minimal intake of at least 2L of water post dosing will be mandatory to ensure a sufficient hydration (250 mL with study drug, then 500 mL between dosing and T4H, 1000 mL between T4H and T12H and 500 ml between T12H and T24H).

1.3.3. *Liver monitoring*

Hepatic enzymes are systematically recorded in phase 1 trials but, considering that at the highest dose tested in the 28-day GLP study in rats (9 mg/kg/day SID), an increase of liver enzymes was observed, and that there is a known important hepatic first pass effect for guanabenz, a strategy will be implemented according the FDA guidance (Drug-Induced Liver Injury: Premarketing Clinical Evaluation) to initiate close observation immediately upon detection and confirmation of early signals of possible impairment of liver function (See Section 3.4.3.1 and 8.10).

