Moreover, the occurrence of moderate adverse reactions within the same system-organ-class in more than one subject, and/or clinically significant changes from baseline measurements will be considered as a safety signal and will have to lead to increase caution and a closer assessment of safety parameters in the other subjects. In such a case, data from all subjects would be to be reviewed.

3.4.3.1. *Liver Chemistry Stopping Criteria*

Liver chemistry threshold stopping criteria have been designed to ensure subject safety and to evaluate liver event etiology (in alignment with the FDA premarketing clinical liver safety guidance).

Study treatment will be stopped **for a subject** if the following liver chemistry stopping criteria is met:

- ALT or AST $\geq 3\text{xULN}$

Refer to Section 8.10, Liver Chemistry Follow-up Procedures, for details of the required assessments if a subject meets the above criteria.

3.4.3.2. *Triglycerides Stopping Criteria*

Several subjects experienced hypertriglyceridemia during the SAD part of the study. All cases were below the threshold of 5.6 mmol/L (i.e. 5 g/L), above which hypertriglyceridemia is considered clinically significant (European Atherosclerosis Society, European Society of Cardiology, French Society of Endocrinology) and no correlation or possible dose relationship was established. Moreover, some subjects with hypertriglyceridemia were in the placebo groups.

Nevertheless, a stopping criterion for triglycerides has been added in the MAD part of the study:

Study treatment will be stopped for a subject if the following criterion is met:

- Serum triglycerides ≥ 5.6 mmol/L and the subject is receiving IFB-088

Study treatment will be stopped for the whole cohort and the dose will not be escalated, if the following criterion is met:

- Serum triglycerides ≥ 5.6 mmol/L in 2 subjects receiving IFB-088.

Next cohort could be administered a lower dose intermediate between the previous cohort and the present cohort.

3.4.3.3. *Renal disorders*

The dose should not be escalated further if one of the circumstances listed below occurs **in 2 or more subjects** within the same cohort:

- Creatinine > 120 $\mu\text{mol/L}$ (1.2 ULN) (Grade 1)
- Or a change from baseline ≥ 30 $\mu\text{mol/L}$ within 24 h
- Or a change from baseline $\geq 50\%$ within one week

(KDIGO definition Ostermann and Joannidis, 2016)

- Hematuria $> 2+$, verified by cytologic exam, on 2 samples and considered at least possibly related to the IMP

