- 12-lead ECGs will be obtained at each time point during the study using an ECG machine that automatically calculates the heart rate and measures PR, QRS, QT, and QTc intervals. Subjects must rest in the supine position for at least 5 minutes before recording. The ECG may be recorded during the period of rest required before the measurements of supine BP and pulse. A qualified physician will review the ECGs promptly and any clinically important finding will be recorded on the appropriate CRF.
- At baseline in Day 1 pre-dose, ECG recordings will be conducted in **triplicate** (with an interval of approximately 10 - 30 minutes). The average value of each parameter will be considered as baseline value.
- ECG recordings will be performed post dose at specified time points (see Flow-Chart Time and Events).
- Parameters:
 - Measured parameters: HR, PR, QRS duration, QRS axis, QT;
 - Derived parameters: two corrections of the QT interval will be investigated: Fridericia's correction (QTcF) and Bazett's correction (QTcB);
 - Observations and comments on the quality of trace, on normality or abnormality.
- Refer to Section [3.4.3.3](#) for QTc withdrawal criteria and additional QTc readings that may be necessary.

Clinical Laboratory Assessments

The following parameters will be determined:

- **Hematology:**

Red blood cell (RBC) count, hemoglobin, hematocrit, white blood cell (WBC) count with differential (neutrophils, lymphocytes, monocytes, eosinophils, basophils), platelets, reticulocyte count.

- **Coagulation:**

Activated partial thromboplastin time (APTT), international normalized ratio (INR).

- **Biochemistry:**

Sodium, potassium, chloride, calcium, total bilirubin, alanine aminotransferase (ASAT), aspartate aminotransferase (ALAT), gamma-glutamyl transferase (GGT), alkaline phosphatases, total protein, albumin, urea, uric acid, bicarbonate, creatine phosphokinase (CPK), creatinine, glycaemia, lactate dehydrogenase (LDH), total cholesterol, HDL and LDL cholesterol, triglycerides.

- **Urinalysis:**

Specific gravity, pH, glucose, protein, blood, nitrites, leucocytes and ketones by dipstick, cytobacteriological exam (if abnormal results on dipstick); beta 2 microglobulin (B2M), proteinuria and creatinuria on urinary sample

- **Other screening tests:**

Hepatitis B antigen (HBs Ag), Hepatitis C antibodies (Anti-HCV Ab), Anti-HIV1 and Anti HIV2 antibodies (only at screening)

- **Alcohol breath test.**

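### Treatment stops for ALT or AST at 3×ULN, but the liver SAE, cohort stop, fixed monitoring and required work-up in Section 8.10 are triggered by ALT only

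*Combined protocol and SAP*

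**What the plan says.** Section 3.4.3.1 stops treatment for an individual subject when ALT or AST is at least 3×ULN, and Appendix 2 repeats that rule. Section 3.4.3.1 then directs: "Refer to Section 8.10, Liver Chemistry Follow-up Procedures, for details of the required assessments if a subject meets the above criteria".

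Section 8.10 opens for anyone who meets that criterion. Its first steps apply to all such subjects: "Immediately withdraw the subject from study treatment", notify the sponsor's medical monitor within 24 hours, complete the follow-up procedures, and stop dosing in the cohort if the event also meets the SAE definition in Section 8.2.

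The procedures themselves come in four blocks. The first two begin "Safety Follow-Up Procedures for subjects with ALT". One sets weekly testing. The other adds raised bilirubin or INR, and then declares the event an SAE, stops the cohort, recalls the subject within 24 hours and sets twice-weekly testing. The third block, the additional work-up, begins "In addition, for all subjects with ALT". The fourth requires autoantibodies and liver imaging when ALT and bilirubin are both raised, "but are optional for other abnormal liver chemistries".

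Section 1.3.3 presents Sections 3.4.3.1 and 8.10 together as the liver strategy, meant to start "close observation immediately upon detection and confirmation of early signals of possible impairment of liver function".

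**The concern.** The criterion that brings a subject into Section 8.10 covers two enzymes, while the actions inside it depend on one. A subject whose AST is at or above 3×ULN while ALT is below 3×ULN (AST-led, for short) is told to complete procedures whose headings do not include him. The plan gives no reason for treating AST differently.

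What is mainly at stake is the SAE label, because it drives action at study level. Under Section 3.4.3, one SAE judged at least possibly related to the product interrupts the study. Under Section 8.3, a serious adverse drug reaction is a New Fact, and dosing is withheld for everyone. For an ALT-led case with raised bilirubin or INR, the SAE label and the cohort stop follow directly from the laboratory values. For the mirror-image AST-led case, someone must first decide that Section 8.2 is met.

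No other rule gives an automatic stop for a single AST-led subject. The laboratory rule in Section 3.4.3 needs two or more subjects, and its transaminase example is above 5×ULN. The safety-signal paragraph in the same section asks for caution and data review, not a stop.

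The plan has its own reason to take liver signals seriously. Section 1.3.3 cites raised liver enzymes at the top dose of the 28-day rat study, and Table 1 records them in the female dog at 6 mg/kg once daily.

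**Working it through.** There is no plan figure to reproduce, because the question is one of trigger logic. The check traces each condition in Section 8.10 for a subject with AST ≥3×ULN and ALT <3×ULN.

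| Step in Section 8.10 | Condition as written | AST-led subject |
|---|---|---|
| Withdraw from treatment, notify medical monitor within 24 h, complete the procedures | Meets 3.4.3.1 (ALT or AST) | Applies |
| Inform cohort and stop its dosing | Meets 3.4.3.1, and event is an SAE under 8.2 | Only if 8.2 is judged to be met |
| Weekly liver tests | ALT ≥3×ULN | Not triggered |
| Automatic SAE, cohort stop, 24 h recall, twice-weekly tests (bilirubin route) | ALT ≥3×ULN and total bilirubin ≥2×ULN, >35% direct | Not triggered |
| The same (INR route) | ALT ≥3×ULN and INR >1.5 | Not triggered |
| Viral serology, PK sample and the rest of the additional work-up | ALT ≥3×ULN | Not triggered |
| Autoantibodies and imaging required | ALT ≥3×ULN and bilirubin ≥2×ULN, >35% direct | Optional |

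**Count of 3×ULN thresholds in 8.10:** 1 (weekly) + 2 (bilirubin and INR routes) + 1 (work-up) + 1 (autoantibodies and imaging) = 5. All five name ALT and none names AST. AST appears twice, both times in a list of tests to repeat.

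**Monitoring interval, MAD part.** Scheduled biochemistry after dosing starts is on Days 3, 6, 10, 13 and 17 (Sections 6.5.4.3 and 6.5.4.5). Follow-up is 7 to 14 days after the last dose (Section 6.5.4.6).

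- Gaps between scheduled tests: 6−3 = 3, 10−6 = 4, 13−10 = 3, 17−13 = 4 days.
- Follow-up window after a Day 14 last dose: 14+7 = Day 21 to 14+14 = Day 28.
- Gap from Day 17 to follow-up: 21−17 = 4 to 28−17 = 11 days.

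The plan does not say whether scheduled laboratory tests continue after treatment is stopped. If they do, a rise found on Days 3 to 13 is rechecked after 3 or 4 days, about the twice-weekly rate, and little is lost in the unit. If they do not, the next fixed test is the follow-up visit, 7 to 14 days after the last dose. In either case a rise found on Day 17 waits 4 to 11 days, and a rise found at follow-up has no fixed recheck. An ALT-led subject would be tested weekly, or twice weekly with raised bilirubin or INR.

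**Illustrative case (assumed values).** AST 4×ULN, ALT 2.8×ULN, total bilirubin 2.5×ULN with 40% direct. Treatment stops and the medical monitor is notified. The SAE label and cohort stop depend on judgment, serology and the PK sample are not required, and autoantibodies and imaging are optional. Exchange the two enzyme values and the SAE and cohort stop become automatic and the whole work-up is required.

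**The case against.** The strongest reply is that Section 8.10 should be read as a whole. It says its procedures apply to anyone who meets the ALT-or-AST criterion and orders that they be completed. The literal reading leaves that order empty for an AST-led subject, so a sensible investigator would apply at least the weekly tier. This has force for weekly testing, where the text is better called ambiguous than silent. It does not reach the automatic SAE or the cohort stop, which rest on a separate, explicit ALT condition.

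The lighter handling might be deliberate. AST can rise from non-hepatic causes, and the plan expressly makes some tests optional for other liver abnormalities. But that line covers autoantibodies and imaging only, and nothing in the plan says AST was meant to be treated more lightly in the other blocks.

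There are other safeguards:

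- The Dose Escalation Committee reviews laboratory data before each subsequent dosing session (Section 3.4.1).
- The investigator may withdraw a subject for safety (Section 7.2).
- Clinically significant abnormal results are followed to normal or baseline, with a cause sought if they persist (Section 6.2).
- Adverse events are followed to resolution (Section 8.7).
- Urgent safety measures and suspension by the sponsor are available (Sections 10.1.6 and 10.2.3).

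These allow action and follow-up, but none supplies an automatic stop or a fixed interval.

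Two further points stand and limit the size of the concern. Study interruption and New Fact status need a causality judgment for ALT-led cases too, so only the SAE label and the Section 8.10 cohort stop are truly automatic. And the plan already reports SAD results, so the remaining planned exposure is 3 MAD cohorts × 6 = 18 subjects on active drug.

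**Conclusion.** The concern holds. On the written text, an AST-led subject stops treatment but falls outside all five thresholds in Section 8.10. If bilirubin or INR is also raised, the SAE label and cohort stop become a matter of judgment where the ALT-led case has them by rule. This should be corrected. It is not a critical flaw, because treatment still stops, the medical monitor is informed within 24 hours, and general follow-up continues.

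The conclusion rests on a literal reading; the authors probably meant to include AST. The Appendix 1 diagram is not in the text available for this review and may name AST. If it does, it would disagree with the wording of Section 8.10, which would still need the change. The documents give no frequency for AST-led cases, so the number of subjects affected cannot be estimated.

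**What to change.** In Section 8.10, change the threshold from ALT to ALT or AST in all five places: the weekly monitoring heading, the bilirubin and INR routes of the SAE block, the additional work-up, and the line on autoantibodies and imaging. This matches the criterion already chosen in Section 3.4.3.1 and Appendix 2. Check that the Appendix 1 diagram says the same. If lighter handling of AST is intended, state it and give the reason.

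The cost is two words in five places, plus an occasional work-up for an AST rise that turns out to be non-hepatic. CPK is already in the routine panel (Section 6.2) to help recognise such a rise, and the SAE block would still need raised bilirubin or INR.

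As a separate clerical correction, the biochemistry list in Section 6.2 attaches the short names ASAT and ALAT to the wrong enzymes. Alanine aminotransferase should be ALAT and aspartate aminotransferase ASAT. The conclusion does not depend on this slip.
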